7 CONVENTIONS

7.1 Derived Dates

Derived dates are defined as follows:

- Study drug start date: earliest complete study medication start date from IP Dosing CRF records with number of tablets taken per day > 0. This is an analysis period reference date.
- Imputed study medication end date: If the study medication end date is (1) noncomplete or (2) complete but before the study medication start date, then the imputed end date is set to the study medication start date. Otherwise, the imputed end date is set to the complete study medication end date. Derived only for IP Dosing CRF records with complete study medication start date and number of tablets taken > 0.
- Study drug end date: latest of (1) complete study medication start dates, or (2) complete study medication end dates from IP Dosing CRF records with number of tablets taken per day > 0.
- Study drug last date
 - Before LSLV database lock: study drug end date derived only for subjects with “yes” or “no” response to the phase completion question on the Treatment Phase Subject Status or Follow-up Subject Status CRF
 - LSLV database lock: study drug end date
- This is an analysis period reference date.
- Last contact date:
 1. Earliest complete death date from the AE CRF, if it exists.
 2. Otherwise, the latest complete date of the following: AE start or end; ECG; informed consent; laboratory test collection; non-study medication start or end; physical exam; physical measurement; procedure; questionnaire; study medication start or end; vital sign; visit.
 3. If the last contact date is after the most recent raw database creation date, then it is set to the most recent raw database creation date.
- Death date: refer to the Core SAP.

No imputations are performed on these derived dates unless otherwise specified.

Refer to the Core SAP for the definition of complete dates.

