At the Baseline Visit, eligibility for continued participation in the study will be assessed before study drug is dispensed. Subjects will be instructed that they must take 1 tablet of study drug (rimegepant 75 mg ODT) each day, and dosing should occur around the same time for each scheduled dose. Subjects may start study drug on the day of the Baseline Visit or the following day, depending on the time of day of their visit. Subjects **must** be instructed that they CANNOT take more than 1 tablet of study drug daily during the Open-label Treatment Phase. If a dose of study drug for a given day is missed, lost, or otherwise unable to be taken, the subject should document that as a missed dose on the study drug wallet and should NOT take the following day's assigned dose until the next calendar day at the specified time.

4.3.2.2 *Week 24 or EOT Visit*

Subjects will return to the study site at the Week 24 Visit (Day 168 +/- 2 days), or at the EOT Visit for early discontinuation, for review of the concomitant medication paper diary, assessment of study drug compliance, and assessment of safety (including vital signs, laboratory tests, and electrocardiography) (Table 1). Subjects must return the unused study drug and concomitant paper diary to the study site.

All subjects **who take study drug and discontinue early from the Open-label Treatment Phase** should complete the EOT Visit. Otherwise, subjects should complete the Week 24 Visit.

In cases where a Week 24 or EOT Visit occurs remotely in order to be completed during the protocol required window and due to the COVID-19 pandemic, the subject should return to the site for the Follow-up Week 2 Visit (2 weeks after the Week 12 or EOT Visit, -2 to +14 days), to

complete all procedures that were not able to be completed remotely. Procedures completed at the Week 24 or EOT Visit occurring remotely do not need to be repeated.

4.3.3 *Follow-up Phase*

The Follow-up Phase will have 2 scheduled visits, Follow-up Week 2, and Follow-up Week 8; These visits should occur approximately 2 weeks and 8 weeks after the Week 24 or EOT Visit, respectively. All subjects ***who take study drug*** should complete both follow-up visits, regardless of completing the Open-label Treatment Phase.

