9.2 Analysis Sets

- Enrolled: Subjects who sign the informed consent form and are assigned a subject identification number.
- Safety: Subjects in the enrolled analysis set who take ≥ 1 dose of study drug (rimegepant).

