4 ANALYSIS SETS, TREATMENT GROUPS, AND SUBGROUPS

4.1 Analysis Sets

The following analysis sets are evaluated and used for presentation and analysis of the data:

- Enrolled: subjects who sign an informed consent form and are assigned a subject identification number, i.e., nonmissing informed consent date. This analysis set is used mainly to assess study population and in by-subject listings.
- Safety: subjects in the enrolled analysis set who take ≥ 1 dose of study drug (rimegepant), i.e., nonmissing study drug start date. This analysis set is used to assess study population, exposure, and on-treatment safety.
 - Follow-up safety: subjects in the safety analysis set whose last contact date is in the follow-up analysis period. This analysis set is used to assess follow-up safety.

See Section 7.1 for derived dates and Section 7.2 for analysis periods.

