6.2.3.1 Subject Disposition From Enrollment to Treatment

The frequency table of subject disposition from enrollment to treatment is provided for the enrolled analysis set based on the Treatment Phase Subject Status CRF, and displays the following categories:

- Treated with rimegepant (identified as subjects with nonmissing study drug start date)

- Not treated with rimegepant (identified as subjects with missing study drug start date)
 - Reasons for early discontinuation (i.e., not completing the study), including not reported. For subjects whose reason is screen failure due to inclusion/exclusion criteria, the reasons for screen failure from the Inclusion/Exclusion Criteria CRF are also included as subcategories.

6.2.3.2 *Subject Disposition During the OLT Phase*

The frequency table of subject disposition during the OLT Phase is provided for the safety analysis set based on the Treatment Phase Subject Status CRF, and displays the following categories:

- Ongoing in the OLT Phase. These are identified as subjects with (1) missing response to the question “Did the subject complete the OLT Phase?” and (2) missing study drug last date. This category only exists before LSLV database lock. After LSLV database lock, subjects with missing response are categorized as “Did not complete the OLT Phase”.
- Completed the OLT Phase. These are identified as subjects with (1) “yes” response to the question “Did the subject complete the OLT Phase?” and (2) nonmissing study drug last date.
- Did not complete the OLT Phase. These are identified as subjects with (1) “no” or missing response to the question “Did the subject complete the OLT Phase?” and (2) nonmissing study drug last date.
 - Reasons for not completing the OLT Phase, including not reported
- Continued to the Follow-Up Phase. These are identified as subjects with “yes” response to the question “Is the subject continuing to the Follow-Up Phase?”.
- Did not continue to the Follow-Up Phase. These are identified as subjects with “no” or missing response to the question “Is the subject continuing to the Follow-Up Phase?”.
 - Reasons for not continuing to the Follow-Up Phase, including not reported.

6.2.3.3 *Subject Disposition During the Follow-Up Phase*

The frequency table of subject disposition during the Follow-Up Phase is provided for the follow-up safety analysis set based on the Follow-Up Subject Status CRF, and displays the following categories:

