7.2 Analysis Periods

Measurements are slotted into analysis periods based on comparing measurement dates to analysis period reference dates (i.e., time is not applicable).

Analysis periods are as follows:

- Pretreatment: This period is used to derive baseline values.
- On-treatment safety: This period is used to assess safety endpoints on treatment for the safety analysis set.
- Follow-up safety: This period is used to assess safety endpoints during follow-up for the follow-up safety analysis set.

Refer to the Core SAP for defining these analysis periods in Phase 2/3/4 multiple-dose (non-randomized non-PRN) studies with 1 treatment phase. See Section 7.1 for derived dates for determining analysis periods.

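### The SAP makes safety-set membership and the start of treatment depend on a complete dosing start date, so a dosed subject with an incomplete date can be counted as untreated or lose early AEs from the tables

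*SAP*

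**What the plan says.** Protocol 9.2 defines the safety set by dosing alone ("Safety: Subjects in the enrolled analysis set who take" at least one dose) and attaches no date condition. SAP 4.1 keeps that wording but adds an operational reading: "dose of study drug (rimegepant), i.e., nonmissing study drug start date". SAP 7.1 derives the date as the "earliest complete study medication start date from IP Dosing CRF records with number of tablets taken per day > 0" and makes it an analysis period reference date. It adds: "No imputations are performed on these derived dates unless otherwise specified". An imputation rule is given for the medication end date of a record; none is given for its start date.

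Three other rules depend on this date:

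- SAP 6.2.3.1 tabulates subjects as "Not treated with rimegepant (identified as subjects with missing study drug start date".
- SAP 7.2 states that "Measurements are slotted into analysis periods based on comparing measurement dates to analysis period reference dates", and that the pretreatment period serves to derive baseline.
- SAP 6.4.1.2 to 6.4.1.4 provide AE tables only for the on-treatment period (safety set) and the follow-up period (follow-up safety set, a subset of the safety set).

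On first dosing, Protocol 4.3.2.1 says: "Subjects may start study drug on the day of the Baseline Visit or the following day".

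**The concern.** The primary objective is safety, and membership of the safety set together with the start of the on-treatment window decides which subjects and AEs are counted. A dosing record can show tablets taken and still lack a complete start date. The SAP allows for this itself: its exposure, compliance and dosing-day derivations (6.2.6.1, 6.2.6.2, 9.2) are all restricted to records with complete start dates. When it happens, the rule gives a result that disagrees with the protocol's definition of a treated subject.

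Short-exposure subjects are the most exposed, because they may have only one or two dosing records. Both documents expect extra early terminations from baseline laboratory elevations (Protocol 9.1, SAP 5), and SAP 6.2.6.2 has a special rule for required tablet counts below 14.

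**Working it through.** **The SAP's own example.** SAP 9.2 has four records with tablets above zero: 01–03 Jan (1 per day), 06–09 Jan (1), 09–11 Jan (2), and 13 Jan with no end date (1). Applying 7.1 and 9.2 reproduces the stated result: start 01 Jan, end 13 Jan, 10 dosing days, 14 tablets.

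**Case 1: no complete start date.** Make every start date in the example partial and leave the end dates alone. No start date can be derived, so the subject is outside the safety set and counted as untreated. SAP 7.1 also accepts complete end dates when it derives the study drug end date, so the same subject still gets an end date of 11 Jan. The rules then yield a last day on drug for someone tabulated as never treated. The subject leaves all AE tables, and also the narrative listings that SAP 6.4.6 limits to the safety set (SAEs, non-serious AEs leading to discontinuation, events of special interest).

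**Case 2: first record partial, later record complete.** Make only the 01 Jan start date partial:

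| | As stated | First start date partial |
|---|---|---|
| Study drug start | 01 Jan | 06 Jan |
| Dosing days | 10 | 7 |
| Tablets | 14 | 11 |
| Time on drug (end − start + 1) | 13 days | 8 days |

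AEs dated 01–05 Jan now precede the reference start, and there is no pretreatment AE table.

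**Size of the shift.** A wallet holds 8 tablets. If one record covers one wallet (an assumption), the derived start is day 1 + 8 = day 9. The example's records last 1 to 4 days, so the shift can be much shorter.

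**Scheduled measurements.** Protocol Table 1 has no visit between Baseline (Day 1) and Week 2 (Day 14 ± 2, so Day 12 at the earliest). A derived start on day 9, or day 10 if dosing began the day after Baseline, is still before Day 12.

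**Effect on reported percentages, planned n = 285.**

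- Case 2 keeps the denominator. An AE term in 15 subjects is 15/285 = 5.26%; with one AE lost it is 14/285 = 4.91%, below the 5% cut in the primary endpoint (before any Core SAP rounding rule).
- Case 1 changes the denominator too. Losing one subject with the event gives 14/284 = 4.93%; losing one without it gives 15/284 = 5.28%.
- The zero-event upper bound, 1 − 0.05^(1/n), is 0.01046 at n = 285 (the SAP states 0.01), 0.01049 at 284 and 0.01064 at 280. Precision is essentially unchanged.

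**The case against.** The strongest reply is that the trigger will hardly occur. Staff mark each wallet with the scheduled dose dates (Protocol 7.2.2), the first dose is due on the Baseline Visit day or the next, returned drug is reviewed at each visit (7.4), and monitors verify CRF data against source (11.1). The first dosing date is therefore among the easiest to settle by query before lock. This stands, and it is why the point is modest.

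It also stands that events are not hidden. AE and death listings (SAP 6.4.1, 6.4.1.1) and the listings of subjects with grade 3 to 4 laboratory results or select LFT elevations (6.4.2) cover the enrolled set. The disposition table also shows a reason for discontinuation for subjects classed as untreated. The definition of a complete date, the exact period boundaries and AE date imputation are in the Core SAP, which is not among the documents; but SAP 4.1 and 7.1 state the membership and start-date rules themselves.

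Three stronger readings are tempting and not supported:

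- That the rule biases the study toward good tolerability. In case 1 the percentage can move either way. Nothing in the documents shows that early stoppers are likelier to have partial start dates, and case 2 needs a later complete record, so it cannot describe a subject who stops within the first record.
- That post-dose values become baseline. Under the 8-day assumption only an unscheduled test could.
- That the SAP discards the protocol's definition. It keeps the dosing wording; the operational rule beside it is what fails.

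**Conclusion.** The point holds as a rule that gives the wrong answer when triggered. A dosed subject with no complete start date is excluded from the safety set, contrary to Protocol 9.2. A subject with a partial first date gets a late start, and AEs in the gap drop out of the tables.

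The likely size is a few subjects or none; no frequency can be taken from the documents. The sample-size precision is not at stake. What can change is whether an individual early event is counted and, occasionally, whether an AE term reaches the 5% cut. In case 2 on-treatment AE counts can only fall or stay the same. The 8-day figure rests on one record per wallet, and the statement about scheduled laboratory, vital sign and ECG baselines rests on a shift of about that length. The repair is cheap and changes nothing if no partial dates occur, so it should be made.

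**What to change.** - **SAP 4.1 and 6.2.3.1:** define treated subjects, and so the safety set, as those with any IP Dosing record showing more than zero tablets, whatever the completeness of its date.
- **SAP 7.1:** if the earliest such record has an incomplete start date, impute the earliest date that fits the partial date and is not before the Baseline Visit. State how the earliest record is identified when its date is incomplete.
- **SAP 6.2.6.1, 6.2.6.2, 7.1 and 9.2:** use the imputed record-level start date in the imputed end date, study drug end date, exposure, compliance and dosing-day derivations. Changing only 4.1 and 7.1's start date would admit subjects with no derivable exposure, and sometimes no end to their on-treatment window. With this step the end date is never missing for a treated subject.
- **Tables:** footnote the number of subjects with an imputed start.

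The cost is a small programming change across these derivations; no new data are needed. The imputation error is about 1 day for subjects who started as Protocol 4.3.2.1 allows. The change does not recover a subject whose tablet count is also unknown.

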7.2 Analysis Periods

Measurements are slotted into analysis periods based on comparing measurement dates to analysis period reference dates (i.e., time is not applicable).

Analysis periods are as follows:

- Pretreatment: This period is used to derive baseline values.
- On-treatment safety: This period is used to assess safety endpoints on treatment for the safety analysis set.
- Follow-up safety: This period is used to assess safety endpoints during follow-up for the follow-up safety analysis set.

Refer to the Core SAP for defining these analysis periods in Phase 2/3/4 multiple-dose (non-randomized non-PRN) studies with 1 treatment phase. See Section 7.1 for derived dates for determining analysis periods.

7.3 Analysis Visit Windows

Refer to Protocol Section 4.3 for the schedule of assessments.

Refer to the Core SAP for defining study days and follow-up days in Phase 2/3/4 multiple-dose (non-randomized non-PRN) studies with 1 treatment phase.

Note that the measurement date must be complete for the measurement to be slotted into an analysis visit.

Analysis visit windows are shown in Table 3.

Table 3 Analysis Visit Windows

Analysis Period		Analysis Day	
Analysis Visit	Abbreviation in Listings	Analysis Visit Window	Target Day
Pretreatment		Study Day	
Screening *		≤ -2	
Baseline *		-1 or 1	
On-Treatment		Study Day	
Week 2		2 to 21	
Week 4		22 to 42	
Week 8		43 to 70	
Week 12		71 to 98	
Week 16		99 to 126	
Week 20		127 to 154	
Week 24		155 to 182	
Extension @	Ext	≥ 183	
Follow-Up		Follow-Up Day	
Follow-Up Week 2		8 to 35	
Follow-Up Week 8		36 to 77	
Follow-Up Extension @		≥ 78	

* For subjects in the enrolled analysis set excluded from the safety analysis set, the visit label is used for slotting.
@ Denotes an extended visit in the analysis period and is displayed primarily in listings

8 CONTENT OF REPORTS

All TLFs described in this SAP are produced for the LSLV final CSR (see Section 1.2).

9 APPENDICES

9.1 Relevant Protocol Deviations

Relevant eligibility protocol deviations include the following categories:

- Treated with study drug under > 1 subject identifier. These subjects are identified from the Protocol Deviations CRF.
- Finding out of range, defined any as any of the following subcategories:
 - Females with a positive pregnancy test during pretreatment (see Section 6.4.2)
 - Estimated glomerular filtration rate (eGFR) according to the re-expressed abbreviated (4-variable) Modification of Diet in Renal Disease (MDRD) Study equation ≤ 40

mL/min/1.73m² during pretreatment, if originally consented to Protocol Version 5 or lower *

- eGFR according to the re-expressed abbreviated (4-variable) MDRD Study equation < 30 mL/min/1.73m² during pretreatment, if originally consented to Protocol Version 6 or higher *
- BMI \geq 33 kg/m² during pretreatment, if originally consented to Protocol Version 5 or lower *
- BMI $>$ 35 kg/m² during pretreatment, if originally consented to Protocol Version 6 or higher *
- C-SSRS suicidal ideation with active intent or plan to act, or suicidal behavior present during pretreatment. Defined as having a “yes” response to any of the following C-SSRS questions during pretreatment:
 - Suicidal ideation question 4 (active suicidal ideation with some intent to act, without specific) or 5 (active suicidal ideation with specific plan and intent)
 - Suicidal behavior question 1 (actual attempt), 3 (interrupted attempt), 4 (aborted attempt), 5 (preparatory acts or behavior), or 6 (suicidal behavior).

For the subcategories marked with “*”, all nonmissing values during the pretreatment analysis period must meet the deviation criteria in order to be considered a deviation.

Relevant subject management protocol deviations include the following categories:

- Study drug dosing noncompliance, defined as any of the following subcategories (see Section 6.2.6.2):
 - Tablet count compliance < 80% from rimegepant start to later of last scheduled OLT Phase visit or rimegepant end
 - > 1 tablet taken on any 1 day.
- Prohibited nonstudy medications, defined as any of the following subcategories:
 - Atypical antipsychotic, divalproex, valproic acid, or valproate taken on or after informed consent #
 - Butterbur root or extract taken up to 14 days before study drug start or afterward
 - Calcitonin gene-related peptide (CGRP) antagonist monoclonal antibody or small molecule taken on or after informed consent #
 - Ergotamine taken on or after informed consent
 - Lamotrigine taken on or after informed consent
 - Narcotic (barbiturate or opioid) taken up to 2 days before study drug start or afterward #
 - Rimegepant taken on or after study drug start
 - Select moderate or strong cytochrome P450 3A4 (CYP3A4) inducer taken on or after informed consent #

- Select strong CYP3A4 inhibitor taken on or after informed consent #.

For the subcategories marked with “#”, preferred names are displayed alphabetically as additional subcategories. Medications taken up to X days before a reference date or afterward are defined as those with imputed medication start date or imputed end date \geq reference date – X . Refer to the Core SAP for additional details about prohibited non-study medications.

The protocol version to which subjects originally consented is determined from the Demographics/Informed Consent CRF.

9.2 Study Drug Dosing Day

A study drug dosing day is defined as a day on which ≥ 1 tablet of study drug was taken.

For each subject, study drug dosing days (i.e., number of tablets per day) are determined for every day in the interval defined from the study drug start date to the study drug end date inclusive.

First, study medication records with complete study medication start date and number of tablets taken per day > 0 are selected. Imputed study medication end date, study drug start date, and study drug end date are derived (see Section 7.1).

Next, records are sorted by study medication start date, imputed study medication end date, wallet ID, and number of tablets taken per day.

Let [study medication start date1, imputed study medication end date1] and [study medication start date2, imputed study medication end date2] denote any 2 records.

Overlapping records are defined as $\max(\text{study medication start date1}; \text{study medication start date2}) \leq \min(\text{imputed study medication end date1}; \text{imputed study medication end date2})$. All days from the maximum to the minimum inclusive are considered overlapping study drug dosing days on which the number of tablets taken per day > 1 . Note that overlapping records need not be consecutive.

Gaps between 2 consecutive records are defined as $\text{study medication start date2} - \text{imputed study medication end date1} \geq 2$ days. All days from the imputed study drug end date1 + 1 day to the study medication start date2 – 1 day inclusive are considered days on which no study drug was taken (i.e., not study drug dosing days).

Example:

Suppose study medication data are as follows for a given subject:

Study Medication Start Date	Study Medication End Date	Imputed Study Medication End Date	Number of Tablets Taken per Day	Note
01JAN2022	03JAN2022	03JAN2022	1	
04JAN2022	05JAN2022	05JAN2022	0	Excluded from analysis
06JAN2022	09JAN2022	09JAN2022	1	
09JAN2022	11JAN2022	11JAN2022	2	1-day overlap with previous record
13JAN2022		13JAN2022	1	1-day gap between previous record

Then study drug start date = 01JAN2022 and study drug end date = 13JAN2022.

Study drug dosing days and number of tablets per day are derived as follows for the subject, taking overlaps and gaps into account:

Date	Number of Tablets per Day	Study Drug Dosing Day Flag
01JAN2022	1	Y
02JAN2022	1	Y
03JAN2022	1	Y
04JAN2022	0	
05JAN2022	0	
06JAN2022	1	Y
07JAN2022	1	Y
08JAN2022	1	Y
09JAN2022	3	Y
10JAN2022	2	Y
11JAN2022	2	Y
12JAN2022	0	
13JAN2022	1	Y

The subject has a total of 10 study drug dosing days and 14 tablets taken.

